### 4) Allergies and Adverse Drug Reaction

- a) History of severe hypersensitivity reactions to other monoclonal antibodies
- b) History of allergy or hypersensitivity to study drug components

### 5) Other Exclusion Criteria

- a) Prisoners or participants who are involuntarily incarcerated. (Note: under certain specific circumstances a person who has been imprisoned may be included or permitted to continue as a participant. Strict conditions apply and Bristol-Myers Squibb approval is required.)
- b) Participants who are compulsorily detained for treatment of either a psychiatric or physical (e.g., infectious disease) illness

Eligibility criteria for this study have been carefully considered to ensure the safety of the study participants and that the results of the study can be used. It is imperative that participants fully meet all eligibility criteria.

### 6.3 Lifestyle Restrictions

Not applicable. No restrictions are required.

## **6.4 Screen Failures**

Screen failures are defined as participants who consent to participate in the clinical study but are not subsequently entered in the study. A minimal set of screen failure information is required to ensure transparent reporting of screen failure participants, to meet the Consolidated Standards of Reporting Trials (CONSORT) publishing requirements, and to respond to queries from regulatory authorities. Minimal information includes date of consent, demography, screen failure details, eligibility criteria, and any serious AEs.

### **6.4.1 Retesting During Screening or Lead-In Period**

Participant Re-enrollment: This study does not permit the re-enrollment of a participant that has discontinued the study as a pre-treatment failure.

## **7. TREATMENT**

Study treatment is defined as any investigational treatment(s), marketed product(s), placebo or medical device intended to be administered to a study participant according to the study treatment allocation.

Study treatment includes only Investigational [Medicinal] Product (IP/IMP).

An investigational product, also known as investigational medicinal product in some regions, is defined a pharmaceutical form of an active substance or placebo being tested or used as a reference in a clinical study, including products already with a marketing authorization but used or assembled (formulated or packaged) differently than the authorized form, or used for an unauthorized indication, or when used to gain further information about the authorized form.

Other medications used as support or escape medication for preventative, diagnostic, or therapeutic reasons, as components of the standard of care for a given diagnosis, may be considered as non-investigational products.

**Table 7-1: Study treatments for CA209870**

Product Description / Class and Dosage Form	Potency	IP/Non-IMP	Blinded or Open Label	Packaging / Appearance	Storage Conditions (per label)
Nivolumab BMS-936558-01 Solution for Injection	100 mg (10 mg/mL and 40 mg/4 mL)	IP	Open Label	Clear to opalescent colorless to pale yellow liquid. May contain particles 240 mg kit contains: 2 x 100 mg vials (10 mL/vial) and 1 x 40 mg vial (4 mL/vial) or carton containing 5 vials of 100 mg	2° to 8°C. Protect from light and freezing

## 7.1 Treatments Administered

The selection and timing of dose for each participant is as follows:

**Table 7.1-1: Selection and Timing of Dose**

Study Treatment	Unit dose strength(s)/Dosage level(s)	Dosage formulation Frequency of Administration	Route of Administration
Nivolumab	240 mg	Q2 weeks	IV

## 7.2 Method of Treatment Assignment

All participants will be assigned to treatment using an Interactive Response Technology (IRT). Users will receive log in information and directions on how to access the IRT. Study treatment will be dispensed at the study visits as listed in Schedule of Activities ([Section 2](#)).

## 7.3 Blinding

This is an open-label, single arm study and blinding procedures are not applicable.

## 7.4 Dosage Modification

### 7.4.1 Nivolumab Dosing

Participants should begin study treatment within 3 calendar days of treatment assignment. Participants should receive nivolumab at a dose of 240 mg as a 30 minute infusion on Day 1 of each treatment cycle until progression, unacceptable toxicity, withdrawal of consent, or study end, whichever occurs first. Nivolumab treatment will be given up to 24 months in the absence of disease progression or unacceptable toxicity. Treatment with nivolumab could be reinitiated as per the initial schedule for subsequent disease progression and administered for up to 1 additional year.

Premedications are not recommended for the first dose of nivolumab. Participants should be carefully monitored for infusion reactions during nivolumab administration. If an acute infusion reaction is noted, participants should be managed according to [Section 7.4.5](#) and [Section 8.1](#).

There will be no dose escalations or reductions of nivolumab allowed. Participants may be dosed within a  $\pm$  3-day window and no less than 12 days from the previous dose during q2w cycles.

Doses of nivolumab may be interrupted, delayed, or discontinued depending on how well the subject tolerates the treatment. Dosing visits are not skipped, only delayed.

Nivolumab Injection, 100 mg/10 mL (10 mg/mL) and 40 mg/mL (10 mg/mL): nivolumab injection is to be administered as an IV infusion through a 0.2-micron to 1.2-micron pore size, low-protein binding in-line filter at the protocol-specified doses. It is not to be administered as an IV push or bolus injection. Nivolumab injection can be infused undiluted (10 mg/mL) or diluted with 0.9% Sodium Chloride Injection, USP or 5% Dextrose Injection, USP to protein concentrations as low as 1 mg/mL. Instructions for dilution and infusion of nivolumab injection may be provided in the clinical protocol, pharmacy binder, or pharmacy reference sheet. Care

must be taken to assure sterility of the prepared solution as the product does not contain any antimicrobial preservative or bacteriostatic agent.

Nivolumab infusions are compatible with polyvinyl chloride (PVC) or polyolefin containers and infusion sets, and glass bottles.

#### **7.4.2      *Dose Delay Criteria for Nivolumab***

Doses of nivolumab may be interrupted, delayed, or discontinued depending on how well the participant tolerates the treatment. Dosing visits are not skipped, only delayed.

Nivolumab administration should be delayed for the following:

- Grade 2 non-skin, drug-related adverse event, with the exception of fatigue
- Grade 2 drug-related creatinine, AST, ALT and/or Total Bilirubin abnormalities
- Grade 3 skin, drug-related adverse event
- Grade 3 drug-related laboratory abnormality, with the following exceptions:
  - Grade 3 lymphopenia or asymptomatic amylase or lipase does not require dose delay
- Dose delay for changes in AST or ALT as follows:
  - If a subject has a baseline AST or ALT that is within normal limits, delay dosing for drug-related Grade  $\geq 2$  toxicity (2 grade shift)
  - If a subject has baseline AST or ALT within the Grade 1 toxicity range, delay dosing for drug-related Grade  $\geq 3$  toxicity (2 grade shift)
  - If a subject has baseline AST or ALT within the Grade 2 toxicity range, delay dosing for a two-fold drug-related increase in AST or ALT or for AST or ALT values  $8 \times$  ULN (whichever is lower).
- Any adverse event, laboratory abnormality, or intercurrent illness which, in the judgment of the investigator, warrants delaying the dose of study medication.

Participants who require delay of nivolumab should be re-evaluated weekly or more frequently if clinically indicated and resume nivolumab dosing when re-treatment criteria are met.

#### **7.4.3      *Criteria to Resume Treatment***

Participants may resume treatment with study drug when the drug-related AE(s) resolve to Grade  $\leq 1$  or baseline value, with the following exceptions:

- Participants may resume treatment in the presence of Grade 2 fatigue
- Participants who have not experienced a Grade 3 drug-related skin AE may resume treatment in the presence of Grade 2 skin toxicity
- For participants with Grade 2 AST, ALT, or TBIL elevation, dosing may resume when laboratory values return to baseline and management with corticosteroids, if needed, is complete.

- Participants with combined Grade 2 AST/ALT AND total bilirubin values meeting discontinuation parameters ([Section 8](#)) should have treatment permanently discontinued.
- Drug-related pulmonary toxicity, diarrhea or colitis must have resolved to baseline before treatment is resumed. Participants with persistent Grade 1 pneumonitis after completion of a steroid taper over at least 1 month may be eligible for retreatment if discussed with and approved by BMS Medical Monitor.

Participants with drug-related endocrinopathies adequately controlled with only physiologic hormone replacement may resume treatment after consultation with the BMS Medical Monitor. Adrenal insufficiency requires discontinuation regardless of control with hormone replacement.

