Select AE categories (events with a potential inflammatory mechanism requiring more frequent monitoring and/or unique intervention such as immunosuppressants and/or endocrine replacement therapy) include: GI AEs, pulmonary AEs, renal AEs, hepatic AEs, skin AEs, and endocrinopathies. In addition, select AEs include a category for infusion reaction. Each category is composed of a discrete set of preferred terms, including those of greatest clinical relevance. These select AEs are considered events of interest based on the mechanism of action and were previously referred to as immune-related AEs or immune-mediated AEs. Most high grade events resolved following the treatment guidelines for the treatment of pulmonary events, GI events, hepatic events, renal events, and endocrine events, respectively. Overall, the safety profile at 3 mg/kg (n = 54) was similar to safety profile across the dose ranges from 0.1 mg/kg to 10 mg/kg (n = 306).

**Table 5.5.1-1: Treatment-related Select Adverse Events by Treatment - All CTC Grades Reported in at least 10 Treated Subjects in CA209003**

Preferred Term	3 mg/kg N = 54		Total (0.1 to 10 mg/kg) N = 306	
	Any Grade	Grade 3 - 4	Any Grade	Grade 3 - 4
Any select AE	23 (43)	2 (4)	140 (46)	19 (6)
Any endocrinopathies	4 (7)	0	29 (10)	3 (1)
Endocrinopathies thyroid	4 (7)	0	26 (9)	2 (1)
Blood TSH increased	2 (4)	0	11 (4)	1 (0.3)
Hypothyroidism	1 (2)	0	11 (4)	1 (0.3)
Any skin AEs	12 (22)	0	75 (25)	1 (0.3)
Rash	5 (9)	0	45 (15)	0
Pruritus	3 (6)	0	32 (11)	1 (0.3)
Any GI AE	7 (13)	0	43 (14)	3 (1)
Diarrhea	6 (11)	0	41 (13)	3 (1)
Any hepatic AE	3 (6)	2 (4)	18 (6)	4 (1)
ALT increased	1 (2)	0	11 (4)	1 (0.3)
Any pulmonary AE	2 (4)	0	17 (6)	6 (2)
Pneumonitis	1 (2)	0	12 (4)	4 (1)
Other select AE	3 (6)	0	15 (5)	2 (1)
Infusion-related reaction	3 (6)	0	12 (4)	0

Abbreviations: AE, adverse event; ALT, alanine aminotransferase; GI, gastrointestinal; TSH, thyroid stimulating hormone  
Source: CA209003. Clinical data cut-off date: 18-Mar-2013

Total includes subjects who also received 0.1 mg/kg (n = 17), 0.3 mg/kg (n = 18), 1 mg/kg (n = 86), and 10 mg/kg (n = 131) in addition to those illustrated at 3 mg/kg (n = 54).

Treatment-related AEs leading to discontinuation were reported in 32 (10.5%) of the 306 nivolumab treated subjects on CA209003. The most frequent of these were pneumonitis (8 subjects; 2.6%) and colitis (3 subjects; 1.0%). There were 3 (1%) drug related deaths; each occurred after development of pneumonitis.

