#### **7.4.6 Protocol-Specific Recommendations for Management of Hepatic Events**

The nivolumab program has developed a standardized approach for the management of hepatic events based on cumulative data across the program in subjects with normal hepatic function. Across most nivolumab studies, the eligibility criteria for inclusion are based on a maximum AST or ALT  $< 3 \times$  ULN; therefore, only subjects with normal to grade 1 LFTs have been enrolled.

For CA209870, the upper limits for inclusion were therefore adjusted to account for baseline liver dysfunction. Subjects with AST or ALT elevations within the CTCAE Grade 2 range are eligible for inclusion. In contrast, the majority of subjects included in prior nivolumab studies have had no higher than a CTCAE grade 1 AST or ALT elevation. Criteria for dose delay, resumption, and discontinuation are in [Section 7.4.2](#), [Section 7.4.3](#), and [Section 8.1](#), respectively. The protocol-specific approach for the management of hepatic events is as follows:

- If AST or ALT levels do not improve with a dose delay of 3-5 days or if the levels worsen, initiate steroid therapy at 0.5-2 mg/kg/day methylprednisolone or oral equivalent.
- For ALT or AST levels  $> 8 \times$  ULN, initiate steroid therapy promptly at 1-2 mg/kg/day methylprednisolone or oral equivalent.
- For all subjects initiating steroids, consult the BMS Medical Monitor within 24 hours after initiation of steroids. Gastroenterology consult is recommended.
- If AST or ALT levels do not improve within 3-5 days or the levels worsen after the start of steroid therapy, discuss with the BMS Medical Monitor the possibility of adding mycophenolate mofetil at 1 g BID.
- Tapering of steroids can start once AST or ALT levels have declined by 1 CTCAE grade. Taper steroids slowly over no less than 1 month.

As outlined in [Section 7.4.3](#), nivolumab therapy may resume when AST or ALT have returned to near baseline unless the criteria for permanent discontinuation are reached ([Section 8.1](#)).

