## **8. DISCONTINUATION CRITERIA**

### **8.1 Discontinuation from Study Treatment**

Participants MUST discontinue investigational product for any of the following reasons:

- Participant's request to stop study treatment. Participants who request to discontinue study treatment will remain in the study and must continue to be followed for protocol specified follow-up procedures. The only exception to this is when a participant specifically withdraws consent for any further contact with him/her or persons previously authorized by participant to provide this information
- Any clinical adverse event (AE), laboratory abnormality or intercurrent illness which, in the opinion of the investigator, indicates that continued participation in the study is not in the best interest of the participant
- Termination of the study by BMS
- Loss of ability to freely provide consent through imprisonment or involuntarily incarceration for treatment of either a psychiatric or physical (eg, infectious disease) illness.

Nivolumab treatment should be permanently discontinued for the following:

- Any Grade 2 drug-related uveitis, eye pain or blurred vision that does not respond to topical therapy and does not improve to Grade 1 severity within the re-treatment period OR requires systemic treatment
- Any Grade 3 non-skin, drug-related adverse event lasting > 7 days or recurs, with the following exceptions for laboratory abnormalities, drug-related uveitis, pneumonitis, bronchospasm, hypersensitivity reactions, infusion reactions, and endocrinopathies:
  - Grade 3 drug-related uveitis, pneumonitis, bronchospasm, hypersensitivity reaction, or infusion reaction of any duration requires discontinuation
  - Grade 3 drug-related endocrinopathies adequately controlled with only physiologic hormone replacement do not require discontinuation
  - Grade 3 drug-related laboratory abnormalities do not require treatment discontinuation except:
    - Grade 3 drug-related thrombocytopenia > 7 days or associated with bleeding requires discontinuation
    - Grade  $\geq 3$  drug-related AST, ALT or total bilirubin requires discontinuation\*
    - Concurrent AST or ALT > 3 x ULN and total bilirubin > 2x ULN

\*In most cases of Grade 3 AST or ALT elevation, study drug(s) will be permanently discontinued. If the investigator determines a possible favorable benefit/risk ratio that warrants

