continuation of study drug(s), a discussion between the investigator and the BMS Medical Monitor/designee must occur.

- Any Grade 4 drug-related adverse event or laboratory abnormality (including but not limited to creatinine, AST, ALT, or Total Bilirubin), except for the following events which do not require discontinuation:
  - Grade 4 neutropenia  $\leq$  7 days
  - Grade 4 lymphopenia or leukopenia
  - Isolated Grade 4 amylase or lipase abnormalities that are not associated with symptoms or clinical manifestations of pancreatitis.
  - Isolated Grade 4 electrolyte imbalances/abnormalities that are not associated with clinical sequelae and are corrected with supplementation/appropriate management within 72 hours of their onset
  - Grade 4 drug-related endocrinopathy AEs, such as adrenal insufficiency, ACTH deficiency, hyper- or hypothyroidism, or glucose intolerance, which resolve or are adequately controlled with physiologic hormone replacement (corticosteroids, thyroid hormones) or glucose-controlling agents, respectively, may not require discontinuation after discussion with and approval from the BMS Medical Monitor.
- Any event that leads to delay in dosing lasting  $>$  6 weeks from the previous dose requires discontinuation, with the following exceptions:
  - Dosing delays to allow for prolonged steroid tapers to manage drug-related AEs are allowed. Prior to re-initiating treatment in a participant with a dosing delay lasting  $>$  6 weeks from the previous dose, the BMS Medical Monitor must be consulted. Tumor assessments should continue as per protocol even if dosing is delayed. Periodic study visits to assess safety and laboratory studies should also continue every 6 weeks or more frequently if clinically indicated during such dosing delays.
  - Dosing delays lasting  $>$  6 weeks from the previous dose that occur for non-drug-related reasons may be allowed if approved by the BMS Medical Monitor.

Prior to re-initiating treatment in a participant with a dosing delay lasting  $>$  6 weeks, the BMS Medical Monitor must be consulted. Tumor assessments should continue as per protocol even if dosing is delayed. Periodic study visits to assess safety and laboratory studies should also continue every 6 weeks or more frequently if clinically indicated during such dosing delays.

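### The protocol gives two answers on stopping for hormone-controlled Grade 4 adrenal insufficiency and on entry with Grade 2 AST/ALT, and no order of precedence among its AST/ALT delay bullets

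*Protocol*

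**What the plan says.** **Adrenal insufficiency.** Section 7.4.3 lets participants whose drug-related endocrinopathy is controlled by physiologic hormone replacement alone return to dosing: they "may resume treatment after consultation with the BMS Medical Monitor". The next sentence reads "Adrenal insufficiency requires discontinuation regardless of control with hormone replacement". It sets no grade limit and offers no approval route. Section 8.1 lists exceptions to the rule that Grade 4 drug-related events end treatment. One exception is "Grade 4 drug-related endocrinopathy AEs, such as adrenal insufficiency, ACTH deficiency" and similar events which, if they resolve or are adequately controlled, "may not require discontinuation after discussion with and approval from the BMS Medical Monitor". For Grade 3, section 8.1 says "Grade 3 drug-related endocrinopathies adequately controlled with only physiologic hormone replacement do not require discontinuation" and does not set adrenal insufficiency apart.

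**Entry with raised transaminases.** Section 6.2 (Physical and Laboratory Test Findings) excludes a screening AST or ALT above 3.0 x ULN. Section 7.4.6 says the limits were adjusted for this trial and that "Subjects with AST or ALT elevations within the CTCAE Grade 2 range are eligible for inclusion". The same section describes other nivolumab studies with a limit below 3 x ULN and concludes: "therefore, only subjects with normal to grade 1 LFTs have been enrolled".

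**Delay for AST/ALT.** The list in section 7.4.2 has one bullet that delays dosing for drug-related Grade 2 AST or ALT with no condition on baseline. A later bullet sets triggers by baseline. With a normal baseline, delay starts at Grade 2. With a Grade 1 baseline, it starts at Grade 3. With a Grade 2 baseline, it starts at a two-fold rise or 8 x ULN, whichever is lower.

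**The concern.** These are participant-safety rules, and a site has to be able to read one instruction from them. A participant with controlled Grade 4 adrenal insufficiency must stop under one section and may continue under another. The Medical Monitor who is consulted has no single rule to apply. A screening transaminase in the Grade 2 range is excluded in one section and eligible in another, and a delay rule has been written for participants whom the exclusion criterion should keep out.

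There is also a link to the analysis. The primary endpoint is the incidence and severity of high-grade treatment-related select adverse events, and section 5.5.1 lists endocrine and hepatic events among the select categories. Dosing continued under one reading could be followed by a worse grade or a new event that would not arise under the other. The documents give no means of sizing that.

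**Working it through.** The check is a comparison of text, plus one scale calculation. The plan gives no figure of its own on this point to reproduce.

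**Step 1. Set the rules side by side.**

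| Situation | One passage | Other passage | Result |
|---|---|---|---|
| Controlled adrenal insufficiency, Grade 4 | 7.4.3: stop | 8.1: may continue with Medical Monitor approval | Direct clash; both name the event |
| Same, Grade 3 | 7.4.3: stop | 8.1: controlled endocrinopathies need not stop | Clash, unless 7.4.3 is read as the exception |
| Same, Grades 1-2 | 7.4.3: stop | 8.1: event not named | One answer only |
| Screening AST/ALT above 3.0 x ULN, in the Grade 2 range | 6.2: excluded | 7.4.6: eligible | Direct clash |
| Drug-related Grade 2 AST/ALT, normal baseline | 7.4.2 general bullet: delay | 7.4.2 baseline bullet: delay | Agree |
| Same, Grade 1 baseline | General bullet: delay | Baseline bullet: no delay before Grade 3 | Depends on precedence |
| Same, Grade 2 baseline | General bullet: delay | Baseline bullet: delay at two-fold rise or 8 x ULN | Depends on precedence |

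**Step 2. Look for a tie-breaker.** None is written. Section 5.5 sends the reader to section 7.4 for delay and discontinuation, while section 7.4.6 sends the reader to section 8.1 for discontinuation. Preferring the specific rule over the general one does not settle Grade 4, because both passages name adrenal insufficiency. The SAP does not help: its programmable eligibility deviations (section 7.2.1) include no AST/ALT item, and its select adverse event section (7.6.6) refers to the Core Safety SAP.

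**Step 3. Is the Grade 2 baseline branch reachable?** No outside grading table is needed, because section 7.4.6 itself ties a limit below 3 x ULN to normal or Grade 1 values. Under section 6.2 the branch is therefore largely empty. The exception would be a later pre-dose value that counts as baseline. Table 2-2 schedules Cycle 1 Day 1 chemistry but does not require a repeat if it was done within 14 days before the first dose. Section 7.4.2 does not say which value is the baseline.

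**Step 4. What does each reading of the delay bullets imply?** If every bullet is a sufficient trigger, the Grade 1 baseline bullet adds nothing. If the baseline bullets govern, a participant going from Grade 1 to Grade 2 is not delayed. The delay trigger for that participant is then Grade 3, which is also the AST/ALT discontinuation trigger in section 8.1.

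**Step 5. Scale of the adrenal point.** The input is Table 5.5.1-1, row "Any endocrinopathies", Grade 3-4, total column: 3 of 306.
- Rate: 3 / 306 = 0.98%; Clopper-Pearson 95% CI 0.20% to 2.84%.
- Per 400 treated: 400 x 0.0098 = 3.9; at the limits, 400 x 0.0020 = 0.8 and 400 x 0.0284 = 11.4.

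The range carries the uncertainty in the rate only; it is not a prediction interval for the count. Adrenal insufficiency has no row of its own, so about 4 (1 to 11) is a ceiling for its Grade 3-4 cases if the earlier rate carries over. Lower-grade cases, which section 7.4.3 also covers, would be additional and cannot be sized. The documents do not give the share of participants with Grade 1 or 2 AST/ALT at baseline, so the entry and delay points cannot be sized.

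**The case against.** The strongest reply is that the direct adrenal clash is confined to Grade 4 and is rare. At Grade 3 the adrenal sentence in section 7.4.3 can be read as a specific exception to the general rule, and at Grades 1-2 there is no second answer. Section 8.1 is permissive and requires Medical Monitor approval, so stopping satisfies both texts and no investigator continues alone. Table 5.5.1-1 also shows thyroid events in 2 of the 3 participants with Grade 3-4 endocrinopathies. That leaves possibly 1 of 306 without one (400 x 1 / 306 = 1.3 per 400, assuming no overlap). The 3 mg/kg column shows 0 of 54, although its exact upper limit is about 6.6%. All of this stands as a limit on frequency and on the grades affected. It does not remove the contradiction, because one section requires stopping with nothing to approve and the other lets the Monitor approve continuing.

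On entry, section 6.2 is the listed criterion, it insists that all criteria be met, and section 9 bars waivers. The documents therefore do not show that sites would enrol against it. That stands too, but section 7.4.6 still says the opposite and the Grade 2 baseline branch depends on the answer.

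On delay, the ordinary reading is that the baseline-specific bullets govern, and the investigator may delay for any laboratory abnormality in any case. That is fair, and this part is an ambiguity, not a contradiction.

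On the endpoint, a participant with drug-related Grade 4 adrenal insufficiency already has a high-grade event. Only a Grade 5 outcome or a new event could add to the count. This supports making no claim of bias.

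Finally, the management algorithms (section 7.4.7) and some liver stopping conditions (section 8.1) are in the Investigator Brochure, which was not available. They might show what was intended, but the conflicting protocol sentences would remain.

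**Conclusion.** The concern holds. Two participant-safety rules contradict each other within the protocol: stopping for controlled adrenal insufficiency (directly at Grade 4, and at Grade 3 unless section 7.4.3 is read as the exception), and entry with Grade 2 AST/ALT. The missing precedence among the delay bullets is a lesser ambiguity.

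This must be fixed because a stopping rule gives opposite instructions for the same participant. The number affected is likely to be small. The estimate of about 4 in 400 assumes that the earlier study's rate, taken across its doses and tumor types, applies to this population and regimen. Medical Monitor involvement reduces variation between sites but does not decide which rule applies.

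**What to change.** Amend protocol sections 6.2, 7.4.2, 7.4.3, 7.4.6 and 8.1, and send a site letter, so that each of these has one answer:

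- stopping for hormone-controlled adrenal insufficiency, at every grade;
- entry with Grade 2 AST or ALT;
- delay at drug-related Grade 2 AST or ALT from a Grade 1 baseline, and from a Grade 2 baseline if that branch is kept.

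In section 7.4.2, state the precedence of the bullets and say whether baseline means the screening or the Cycle 1 Day 1 value. Make the Grade 2 baseline branch agree with whichever entry limit is kept. As a minor tidy-up, use one wording for AST/ALT resumption: section 7.4.3 requires a return to baseline, whereas section 7.4.6, which refers back to it, accepts a value close to baseline. Check the result against the Investigator Brochure algorithms. Which clinical rule is kept is for the sponsor's medical team, and this review takes no position on it.

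The cost is amendment text, a site letter, and ethics approval (with local health authority approval where applicable) before implementation. Under Appendix 2, consent must be revised if the change increases potential risk or substantially alters the design. No visits, tests or participants are added.
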